7.11 Secondary Endpoint Analysis

The secondary endpoint hypothesis will be tested only after the primary endpoint of the study is met. The secondary hypothesis will be evaluated using the proportion of responders on the primary outcome measure at 13 weeks. A responder is defined as having improvement in NOSE Scale score of $\geq 20\%$ from baseline or at least one NOSE Scale class improvement.

The hypothesis will be tested at the 1-sided alpha .025 level with a single proportion binomial test. The responder proportion (percent) will be presented with the associated 95% confidence interval. The secondary endpoint will be met if the lower bound of the confidence interval exceeds 0.55 (55%).

The frequency (proportion) of septal perforation will be calculated along with the 95% confidence interval along with a summary of each event.

Clinical Study Protocol – SWELL Study

The frequency (proportions) of serious device-related adverse events and procedure-related adverse events will be calculated along with the 95% confidence interval along with a summary of each serious event.

7.12 Other Outcome Measures Analyses

Additional outcome measures will be collected for information and hypothesis generating purposes. The primary analysis methods will be descriptive and exploratory and presented by evaluation to more completely understand the time course of treatment effect. Measures will be summarized using frequencies and percentages for categorical measures and mean, median, SD, minimum and maximum for continuous factors. Statistical comparisons will either not be performed or used for information purposes. Proportions may be compared using exact tests, chi-square tests, or general linear models. Continuous outcomes may be compared using t-tests or nonparametric equivalents. Repeated measures linear mixed models may be used for longitudinal analysis across evaluations.

Other outcome measures include:

- Nasal Assessment - The visual and endoscopic assessment factors will be summarized to include frequency and percentage of responses in each category for each component of the nasal assessment by treatment group at screening, just prior to procedure (if screening and procedure occur on different days), immediately after procedure and at 3 months. The distribution of SSB grades prior to the procedure and at each follow-up will be summarized along with the mean scores and change from screening.
- Radiographic Imaging - A subset of study sites will be selected to participate in a substudy of the use of CT imaging to assess changes in the SBB after treatment. SSB measures from CT scans will be summarized and presented as means at screening and at 3 months and as the mean change from screening to 3 months.
- NOSE Scale score - Categorical responses and scores on the NOSE Scale and its individual components will be subject to multiple summary methods and analyses including the:
 - Mean and mean change from preprocedure at the 3-, 6-, 12-, 24- and 36-month follow-up evaluations.
 - Distribution of NOSE Scale score severity categories (mild, moderate, severe, extreme) at the 3-, 6-, 12-, 24- and 36-month follow-up evaluations for each group.
 - Mean, change from preprocedure in mean, and response distribution of the 5 components of the NOSE Scale score (nasal congestion, nasal blockage, trouble breathing, trouble sleeping, and getting enough air during exercise) at the 3-, 6-, 12-, 24- and 36-month follow-up evaluations for each group.

Clinical Study Protocol – SWELL Study

- Proportion of responders based on improvement in NOSE Scale score at the 3-, 6-, 12-, 24- and 36-month follow-up evaluations for each group.
- VAS for nasal pain- Summary will include mean NRS pain scores assessed postprocedure.
- NRS for ease of breathing - Summary will include mean and mean change from baseline (screening) of ease of breathing scores assessed at screening and at each follow-up evaluation.
- SNOT-22 - mean and change from baseline (screening) in mean SNOT-22 score and individual domain scores will be summarized at the 3-, 6-, 12-, 24- and 36-month follow-up evaluations.
- Participant Satisfaction Assessment - mean response for each of the 5 survey questions will be summarized at the 3-, 6-, 12-, 24- and 36-month follow-up evaluations.
- Medications - Medication, and other therapies associated with relief or treatment of NAO symptoms will be documented at screening and updated as necessary with changes to any treatment and any new associated medications at each postprocedure evaluation. An increase or decrease in frequency of use or dose, no change, starting new or stoppage of medication use compared to the first recorded use will be documented.

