4.2 Secondary Objective

The secondary objective is to evaluate the durability of the treatment effect in an extended follow-up period of 36 months.

In addition to the primary and secondary endpoints, both the primary and secondary objectives will be supported by assessment of several other effectiveness and safety measures that will include:

- Adverse events - Incidence (type and category) of adverse events overall and by follow-up interval.
- Nasal Assessment - The target SSB within each nostril will be visually assessed at screening, prior to the procedure, immediately after the procedure, and 3 months after the procedure. The use of an endoscope for visual assessment is required. Representative endoscopic video of each nasal passage will be captured for each assessment. Endoscopic nasal assessment will include assignment of an SSB grading score.³⁶
- CT Assessment – A subset of study sites will be selected to participate in a substudy of the use of CT imaging to assess changes in the SBB after treatment. Radiographic changes, including change in size of the SSB, will be assessed using CT imaging prior to the procedure and at 3 months after the procedure.
- NOSE Scale score:
 - Mean and mean change from screening at the 3-, 6-, 12-, 24- and 36-month follow-up evaluations.
 - Distribution of NOSE Scale score severity categories (mild, moderate, severe, extreme) at the 3-, 6-, 12-, 24- and 36-month follow-up evaluations.
 - Mean, change from screening in mean, and response distribution of the 5 components of the NOSE Scale score (nasal congestion, nasal blockage, trouble breathing, trouble sleeping, and getting enough air during exercise) at the 3-, 6-, 12-, 24- and 36-month follow-up evaluations.
 - Proportion of responders based on improvement in NOSE Scale score at the 3-, 6-, 12-, 24- and 36-month follow-up evaluations.
- Visual Analog Scale (VAS) for nasal pain - perception of pain associated with the procedure on a 0 to 100 mm scale (0 indicating no pain and 100 indicating the worst pain ever) assessed immediately after treatment and at 1 week.
- Numeric Rating Scale (NRS) for ease of breathing through the nose - perception of the ability to breathe through the nose over the past week on a 0 to 10 scale with 0 indicating no difficulty and 10 indicating extreme

Clinical Study Protocol – SWELL Study

difficulty assessed at screening and the 3-, 6-, 12-, 24- and 36-month follow-up evaluations.

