5.2.1 Inclusion Criteria

1. Age 22 to 85 years (inclusively).
2. Seeking treatment for nasal obstruction and willing to undergo an office-based procedure.
3. Baseline NOSE score ≥ 55 .
4. Presence of SSB hypertrophy limiting visualization of the middle turbinate (MT) by more than 50%.
5. Reduction in size of the SSB after application of topical decongestant on a cotton plug directly to the SSB region.
6. Improvement in the symptoms of nasal obstruction after SSB decongestion suggesting that the SSB may play a role in nasal obstruction.
7. Willing and able to withhold anticoagulant medications during the perioperative period (3-day window on either side).
8. Willing and able to provide informed consent.
9. Willing and able to comply with the participant-specific requirements outlined in the study protocol.

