5.4 Outcome Measures

5.4.1 Nasal Assessment

The targeted nasal area within each nostril will be visually assessed for this study. The use of both visual and endoscope assessment is required. Observations are categorized as not present, mild, moderate, or severe. Representative endoscopic video of each nasal passage will be captured for each assessment.

General assessments include:

- Saddle nose deformity
- Bruising around orbital area
- Soreness, pain
- Numbness.

Endoscopic assessments:

- Inflammation / generalized redness
- Swelling, edema
- Blanching (generalized whiteness)
- Bleeding at anesthetic injection site (not requiring physician intervention) immediately postprocedure only
- Bleeding at treatment site (not requiring physician intervention) immediately postprocedure only
- Nasal obstruction from tissue edema

Clinical Study Protocol – SWELL Study

- Disruption of mucosal flow / crusting
- SSB endoscopy grading score. The SSB endoscopy grading scale was developed by Catalano et al.³⁶ to complement the more subjective NOSE Scale for the purpose of evaluating the degree of reduction of the SSB as seen clinically and is based on the ability to see the middle turbinate from the most anterior nares during endoscopy. Scores are assigned as:
 - 1 = visualization of >50% of the ipsilateral middle turbinate
 - 2 = visualization of <50% of the middle turbinate
 - 3 = no visualization of the middle turbinate.

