6.1 Schedule of Events

Activity / Assessment	Screening	Treatment			Follow-up (in-office)		Extended Follow-up (remote)			
		Preprocedure	Procedure	Immediate Postprocedure	1 Week	3 Months (13 weeks)	6 Months (26 weeks)	12 Months (52 weeks)	24 Months (104 weeks)	36 months (156 weeks)
Window (days)	(-30)	(0)		(± 3)	(± 14)	(± 30)	(± 30)	(± 30)	(± 30)	(± 30)
Eligibility	X									
Consent	X									
Demographics / Medical History	X									
Physician Evaluations										
Nasal Assessment (visual, endoscopic)	X	X ¹		X	X	X				
CT imaging of SSB	X ²					X				
Current medication use (study relevant)	X			X ³	X	X	X	X	X	X
Participant Evaluations										
NOSE Scale	X ⁴					X ⁵	X	X	X	X
VAS nasal pain				X	X					
NRS ease of breathing	X					X	X	X	X	X
Participant Satisfaction Survey						X	X	X	X	X
SNOT-22	X					X	X	X	X	X
Study Procedure (includes anesthesia)			X							
Adverse Events	X			X	X	X	X	X	X	X

¹ Nasal Assessment do not need to be repeated if Screening and Treatment visits occur on the same day.

[figure not shown]
² CT should only be performed if your site was selected for the CT substudy and only after all other screening procedures and participant eligibility is confirmed.

³ Add any postprocedure medications to the medication log.

⁴ Baseline NOSE Scale Score for analysis is defined as the Screening score.

⁵ Primary analysis endpoint evaluation.

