6.4 Treatment Visit and Procedure (Day 0)

The treatment is summarized below and is comprised of the preprocedure, procedure and postprocedure as indicated on the Schedule of Events ([Section 6.1](#)). The treatment visit should occur within 30 days of the Screening Visit (study entry), once all inclusion and exclusion criteria have been met. Consult the Aerin Console Instructions for Use (IFU) for full detail of the standard treatment procedure and step-by-step instructions for preparation and use of the Vivaer ARC Stylus and Aerin Console.

Clinical Study Protocol – SWELL Study

Preparation (preprocedure)

The treatment will be performed in the study clinic within 30 days of study entry. The participant will be seated and positioned in the exam chair according to personal comfort and study physician's preference (eg, upright, reclined or supine). A nasal assessment (visual and endoscopic exam) will be performed on each side of the nose and for each nostril, including endoscopic video. This is to assess the configuration of the structural components of the lateral nasal wall (including the upper and lower lateral cartilage, their junction and the overlying mucosa), location of SSB and the MT to allow the study physician to map out and plan the areas of treatment. If the Screening and Treatment visits occur on the same day, the nasal assessment does not need to be repeated for Preprocedure.

Following the nasal assessment, it is recommended the study physician prepare the treatment area with a topical anesthetic agent (eg, lidocaine, tetracaine, etc.) and applying via spray, gel, or saturated pledget placed within the nose. After an appropriate amount of time, the SSB is then visualized with an endoscope and infiltrated in a submucosal plane with a small amount of local anesthetic to provide adequate tissue analgesia as well as tumescence to facilitate radiofrequency energy transfer. For example, cottonoid pledges saturated with 4% lidocaine are placed in the nasal passages adjacent to the septum; after 5 minutes, these pledges are removed and the swell body is injected bilaterally with 0.4 cc of 1% lidocaine with 1:100,000 epinephrine on each side.

Treatment administration

Once the nasal cavities have been anesthetized, participants will undergo bilateral treatment of the SSB in a single study procedure session. Each side of the nose will be treated as follows

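### SSB grade change is measured from the screening grade that in effect decides eligibility, so regression to the mean can modestly flatter the descriptive endoscopic result; the target nostrils are also unstated

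*Combined protocol and SAP*

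**What the plan says.** **Change.** For the nasal assessment, Section 7.12 states that "SSB grades prior to the procedure and at each follow-up will be summarized along with the mean scores and change from screening". Screening is the only reference point named for change.

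**Eligibility.** Criterion 4 in Section 5.2.1 requires "Presence of SSB hypertrophy limiting visualization of the middle turbinate (MT) by more than 50" per cent. It does not say whether one side or both must qualify.

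**Scale.** Section 5.4.1 grades each side on three levels: "1 = visualization of >50% of the ipsilateral middle turbinate", grade 2 is less than half visible, and grade 3 is none visible. Lower is better.

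**Who is treated and graded.** Section 6.4 says "participants will undergo bilateral treatment of the SSB in a single study procedure session". Section 4.2 says "The target SSB within each nostril will be visually assessed at screening, prior to the procedure, immediately after the procedure, and 3 months" after it, and that "Endoscopic nasal assessment will include assignment of an SSB grading score".

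**The second pre-treatment grade.** Section 6.4 places a pre-procedure endoscopic assessment before any anesthetic, but with a waiver: "If the Screening and Treatment visits occur on the same day, the nasal assessment does not need to be repeated for Preprocedure". Footnote 1 of the schedule in Section 6.1 repeats the waiver, and Section 7.12 tabulates the pre-procedure assessment only when the two visits are on different days.

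**Unit and status.** Section 7.5 says only that some evaluations will be summarized by nostril. Section 7.12 calls these outcomes descriptive and exploratory. Section 5.5.2 defines study success on mean NOSE improvement alone.

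**The concern.** Hiding more than half of the turbinate means seeing less than half of it, which is grade 2 or 3. Participants therefore enter because a screening view fell on the wrong side of a cut-off, and change is counted from that same view. Some of those views will have been poor by chance: reader variation, scope position, or a swell body that happened to be congested that day. Section 1.0 describes the tissue as vasoerectile and responsive to histamine, so day-to-day variation is plausible. On re-reading, such nostrils look better without any treatment effect. With no control arm (Section 5.1), nothing subtracts this.

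The second issue is which nostrils the mean covers. If one qualifying side suffices, the other may be grade 1 and cannot improve. Section 1.0 reports that the swell body is more prominent opposite a septal deviation, and exclusion 2 removes only severe deviation judged the primary contributor and warranting surgery, so asymmetry is to be expected.

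The stake is limited but real. Section 5.4.1 presents the grade as a complement to the more subjective NOSE Scale, and CT measurement is confined to selected sites. Elsewhere the grade is the only planned measure of swell body size.

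**Working it through.** **No figure to reproduce.** The plan states no reliability, expected change or power for the SSB grade. The sizes below are illustrations on assumed inputs.

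**1. Regression to the mean, no treatment effect.**

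Assumptions: true visible turbinate fraction has mean 45 and SD 25 percentage points; each reading adds independent error with SD 5, 10 or 15; between-side correlation is 0.3 to 0.8; a participant enters if at least one nostril reads below 50 at screening. Each nostril is graded at screening (S), pre-procedure (P) and follow-up (F). Change is F − S as planned, or F − P.

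| Summary | Error SD 5 | SD 10 | SD 15 |
|---|---|---|---|
| All treated nostrils, F − S | about −0.03 | about −0.05 | about −0.07 |
| Nostrils at grade 2 or 3 at screening, F − S | −0.075 | −0.145 | −0.207 |
| Those nostrils returning to grade 1 untreated | 7.5% | 14.5% | 20.5% |
| Either set, F − P | 0.00 | 0.00 | 0.00 |

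Across the assumed correlations the first row spans about 0.03 to 0.08.

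**2. Why the two F − S rows differ.** Grade 1 nostrils were selected in the opposite direction and regress upward. A second model, with a latent size and two cut-offs, shows the offset. At 64% repeat agreement and between-side correlation 0.3, 23.4% of nostrils are grade 1 at screening, qualifying nostrils change by −0.169 and grade 1 nostrils by +0.345:

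(1 − 0.234) × (−0.169) + 0.234 × 0.345 = −0.129 + 0.081 ≈ −0.05.

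Over repeat agreement of 53% to 81%, that model gives −0.03 to −0.09 over all nostrils when one side suffices. If both sides had to qualify there is no offset, and it gives −0.06 to −0.24. Criterion 4 does not settle which applies.

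**3. Dilution.** If affected nostrils truly fall by d and a fraction f of nostrils is grade 1 with no change, the overall mean change is −d(1 − f). With d = 0.8 (assumed):

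- f = 10%: −0.8 × 0.90 = −0.72
- f = 25%: −0.8 × 0.75 = −0.60
- f = 50%: −0.8 × 0.50 = −0.40

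Changing the baseline reading does not alter this.

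**4. Choosing and measuring on the same reading.** If affected nostrils are instead those at grade 2 or 3 on the pre-procedure grade, and change is also taken from that grade, the first model again shows false improvement: about −0.06 to −0.18 grade, with 7% to 24% of untreated nostrils improving. Choosing on S and measuring F − P gives 0.00.

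**The case against.** The strongest reply is that this is an exploratory outcome with no hypothesis test, and that Section 7.12 already tabulates grades before the procedure and at follow-up, so a careful reader could see the pre-procedure distribution. That stands and limits the severity. It does not repair the change score, because marginal distributions do not show within-nostril change.

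Four stronger readings are tempting, and the documents do not support them.

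- *The endoscopic effect is biased in two opposing directions.* Only the first mechanism is bias, and its size depends on grading error that the documents do not report. Both sides are treated in every participant, so the mean over all treated nostrils is a legitimate target; including grade 1 nostrils dilutes it.
- *A cleaner baseline exists for everyone.* It does not: "Nasal Assessment do not need to be repeated if Screening and Treatment visits occur on the same day". The same-day share is not given, and for those participants the screening grade is the only one.
- *The decongestant test contaminates the screening grade.* The documents do not give the order. Criterion 5 requires seeing the swell body shrink, so a view before decongestant must exist. A grade taken afterwards would understate later improvement.
- *The remedy is to report the proportion improving among nostrils at pre-procedure grade 2 or 3.* That brings regression to the mean back, as step 4 shows.

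**Conclusion.** The concern holds in a limited form. Measuring change from the screening grade, which in effect decides criterion 4, can exaggerate descriptive improvement: about 0.03 to 0.08 grade over all treated nostrils if one qualifying side is enough, and 0.08 to 0.21 in nostrils that qualified at screening. The direction follows from the design. The sizes rest on assumed reading-error SDs of 5 to 15 points and an assumed spread of turbinate visibility.

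The 0.00 from the pre-procedure grade assumes errors independent between visits. A congested spell lasting through both visits would leave some regression behind.

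Dilution by grade 1 nostrils is a separate matter of an unstated target. A reader should not infer that the primary analysis or study success is affected. Severity: CONSIDER.

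**What to change.** In Section 7.12:

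1. Where screening and treatment are on different days, measure SSB grade change from the pre-procedure grade.
2. Show same-day participants separately, with the screening grade as baseline and a note that regression to the mean remains in their change score.
3. Make the nostril the reporting unit. Give results for all treated nostrils and for nostrils at grade 2 or 3 at screening. Choose the second set on the screening grade and, for different-day participants, measure its change from the pre-procedure grade. Do not choose and measure on the same reading.
4. Optionally add a per-nostril shift table of baseline grade by 3-month grade.

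The cost is analysis wording only: no new visits, data or participants. The drawbacks are two baseline sources that must be labelled, and fewer nostrils in the cleaner summary, by a number that depends on the unknown same-day share.

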7.13 Subgroup Analysis

A subgroup analysis of primary and secondary efficacy measures based on allergic or nonallergic classification will be performed for the 3-month endpoint using a 2-sample t-test to compare changes in mean NOSE Scale score between the 2 groups and a 2 sample binomial or exact test to compare the responder percents between the 2 groups.

Other exploratory subgroup analyses may be performed based on demographic, procedural, or other identified characteristics. Potential baseline covariates with possible impact on outcomes at 3 months are:

- Age
- Race
- Sex
- BMI

7.14 Safety Analysis

All adverse events, collected from the time of study consent (study entry) until the end of the study will be analyzed for all participants. Adverse events may occur during the treatment phase or during the follow-up phase. AEs occurring after the screening assessment but before the procedure (application of anesthesia) will be

Clinical Study Protocol – SWELL Study

documented in the participant's medical record and EDC but will not count as related to the study device or procedure. Adverse events will be coded using a custom Aerin Medical dictionary so that adverse events may be categorized for analysis at an appropriate level of detail. Listings will be provided to detail individual events. The number of participants, number of AEs, and the proportion of participants reporting each AE will be summarized. Seriousness and severity of AEs and their relationship to the device and procedure will be summarized. A time course of adverse events will be presented. Any unexpected adverse device experiences or adverse events that occur at an unexpectedly high incidence rate will receive detailed analyses. Narratives will be presented for all deaths, serious adverse events, unexpected adverse device experiences, and participants withdrawn due to an adverse event.

